1.3.2 Delayed Intervention (Control) Arm

	All participants	All participants will as per site standa	Once clusters/sites are switched, follow		
		Participants with a quantifiable HCV RNA	All other participants	procedures for the Intervention Arm.	
Study Visit	Screening ⁴	Registration ⁵	N/A		
Study Weeks	0	0	N/A		
Visit Window (weeks, min to max)	0	N/A	N/A		
Informed consent	X				
Behavioural questionnaire	X				
(Screening version)					
EQ-5D-5L	X				
Health economics questionnaire	x				
Testing acceptability questionnaire ¹	х				
HCV RNA and/or Ab ²	Х	X			
HCV result notification ³	х	х			
Treatment ⁴		X			
Research Samples					
Dried blood spot	X				

Key	
1	Testing acceptability questionnaire will be completed in the control arm only.
2	Participant will be referred for HCV testing (standard of care).
3	Standard of care arm: The result will be delivered as per site local procedure.
	Refer to section 10.2 for additional details.
4	For participants with a quantifiable HCV RNA who do not initiate treatment in the control
	arm (standard of care), they can be re-screened in the delayed intervention arm 3 months
	after their date of screening.
5	Data will be collected on participants with a quantifiable HCV RNA and those who initiate
	HCV treatment.

2.0 Background and rationale

Viral hepatitis is the 7th leading cause of mortality globally, having surpassed the number of annual deaths due to HIV, malaria, and tuberculosis¹. Globally, 71 million people are living with hepatitis C virus (HCV), with 6.1 million having recently injected drugs², and an additional burden among former people who inject drugs (PWID). In Australia, the majority of existing (80%) and new (90% of 9,000 annually) cases are in PWID^{3,4}. The advent of simple, well-tolerated, direct-acting antiviral (DAA) HCV therapies with cure rates >95% is one of the most exciting medical advances in decades⁵. Successful therapy leads to improved quality of life and reduced morbidity/mortality⁶, providing an opportunity to reverse the rising burden of advanced liver disease.

The World Health Organization (WHO) has set a goal to eliminate HCV as a global public health threat by 2030, with targets to increase HCV diagnoses and treatment, and reduce new infections and liver-related mortality⁷. However, among the 71 million people with HCV worldwide, less than 20% have been diagnosed and less than 10% have received treatment⁸. In Australia, HCV DAA treatment uptake initially exceeded expectations (2016: 32,400 treated; 14% with HCV). But, the number of people initiating therapy has continued to decline (2017: 21,370; 2017: ~2,000/month; 2018: ~1,400/month). Improving HCV testing and treatment to reduce disease burden is a key aim of global and national HCV strategies^{9,10}.

Globally, HCV testing and diagnosis remains inadequate¹¹. Current testing algorithms involve detection of HCV antibodies to confirm exposure, followed by HCV RNA testing to detect active infection. This two-step pathway requires up to 5 visits to practitioners and off-site phlebotomists, leading to a drop-off in those receiving a diagnosis of active infection¹². Standard of care HCV testing is also limited by a lack of on-site phlebotomists (requiring off-site referral) and poor venous access (a major problem among people who inject drugs). In Australia, 81% have had an antibody-based HCV diagnosis, but only 47% have been tested for active infection¹². As highlighted in the 4th National HCV Strategy, a Priority Action is to "improve referral and access to high quality support services at the time of diagnosis for people with HCV to initiate a pathway to care".

In a systematic review of interventions to improve HCV care among PWID led by our group ¹³, key interventions to enhance HCV testing (on-site testing; and dried blood spot testing), linkage to care (facilitated referral for HCV assessment) and treatment (integrated HCV care) were identified. Studies were limited by small sample sizes, and the lack of randomized controlled trials or comparative studies in the DAA era. Well-designed studies evaluating interventions to enhance HCV testing/treatment among PWID are needed.

Dried blood spot testing can enhance HCV testing and linkage to care^{13,14}. Benefits of dried blood spots include: 1) avoiding the need for phlebotomy; 2) enables testing for HCV antibodies (exposure) and RNA (active infection); 3) easy to transport/store; 4) can test for other viruses (e.g. HIV); 5) sample collection can be performed by peers or self-collection¹¹. Also, dried blood spot testing has excellent sensitivity and specificity for the detection of active HCV ¹⁵.

Point-of-care HCV testing has also been demonstrated to increase testing and linkage to care ¹⁴. Our group led the first evaluation of a finger-stick point-of-care HCV RNA assay^{16,17} as part of a clinical observational study in drug treatment clinics and needle and syringe programs (NSPs), enabling same-day diagnosis of active infection (HCV RNA) in one hour (sensitivity and specificity, 100%)¹⁷. The findings have informed regulatory approval submissions in Europe and Australia. The next step is to translate this novel discovery into routine clinical practice. There is an unprecedented opportunity to evaluate whether finger-stick point-of-care HCV RNA testing could be integrated into routine practice to enhance HCV testing and treatment among PWID.

Settings for HCV care for PWID include hospitals, primary care, drug treatment clinics, and prisons¹⁸. But, there is a need to link less service-connected PWID to HCV care. In Australia, there is broad NSP access (3,627 NSPs; 98 primary sites)¹⁹ and PWID regularly attend NSPs to collect injecting equipment. NSPs offer an opportunity to engage with PWID who may not be engaged in health services. Further, on-site testing improves linkage to HCV treatment¹³. As highlighted in the *National HCV Strategy*, "Peer support programs offering education may improve engagement in HCV assessment/treatment²⁰" and "The role of peer educators to increase testing should be explored. Such services should be linked to peer-based drug-user organisations...and NSPs."

The TEMPO study will compare point-of-care HCV RNA testing, dried blood spot testing, and standard of care as strategies to enhance HCV treatment uptake among people with HCV and recent injecting drug use attending NSP services.

3.0 Hypotheses

Compared to standard of care, an intervention consisting of either dried blood spot testing or point-of-care HCV RNA testing, will lead to an increased proportion who initiate HCV treatment among people with HCV and recent injecting drug use attending NSP services.

Compared to dried blood spot testing, point-of-care HCV RNA testing will lead to an increased proportion who initiate HCV treatment at 12 weeks following enrolment among people with HCV who have recently injecting drug use attending NSP services.

4.0 Study objectives

4.1 Primary objective

To compare the proportion of HCV RNA positive participants who initiate HCV treatment at 12 weeks following enrolment between those who receive point-of-care HCV RNA testing, dried blood spot testing, and standard of care.

4.2 Secondary objective(s)

Among those who receive point-of-care HCV RNA testing, dried blood spot testing, and standard of care:

- 1. To compare the time to HCV DAA treatment initiation among those who initiate treatment.
- 2. To compare the proportion of HCV RNA positive participants who initiate HCV DAA treatment at 24 weeks following enrolment.
- 3. To compare the proportion of HCV RNA positive participants who initiate HCV DAA treatment at 12 months (52 weeks) following enrolment.
- 4. To compare the proportion of participants who complete HCV DAA treatment.
- 5. To compare the proportion of participants who achieve an SVR (defined as HCV RNA below the lower limit of quantitation at post treatment week 12).
- 6. To compare the proportion of participants who are HCV RNA negative at 12 weeks.
- 7. To compare the proportion of participants who are HCV RNA negative at 24 weeks.
- 8. To compare the proportion of participants who are HCV RNA negative at 12 months (52 weeks).
- 9. To evaluate the incidence of HCV reinfection following successful HCV therapy.
- 10. To compare the cost-effectiveness of these different testing strategies.

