7.1.4 Eligibility criteria for treatment

Participants who have a quantifiable HCV RNA will be assessed for treatment eligibility. Those in the point-of-care arm will be able to complete the treatment work-up on the day of HCV screening. Those in the control arm and dried blood spot arm will have treatment work-up as per standard of care once the HCV RNA test results are received from the laboratory.

Treatment uptake is expected to be higher at 12 weeks following enrolment in the point-of-care arm (45%) compared with the dried blood spot arm (20%) or control arm (10%).

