HCV RNA negative participants will have no further assessments or visits as part of the study protocol. Participants who are HCV RNA positive will be enrolled in the cohort. Screening in the intervention arm will continue until a total of 220 HCV RNA positive participants (~20 participants per site) are enrolled in the intervention arm (either dried blood spot and point-of-care). In the delayed intervention arm, 220 HCV RNA positive participants (~20 participants per site) will be enrolled in the control (standard of care) phase and then clusters/sites will be switched to intervention (either dried blood spot and point-of-care) – at which screening will continue until a

total of 220 HCV RNA positive participants (~20 participants per site) are enrolled. Hence a total of 660 HCV RNA positive participants will be enrolled in the study.

Participants with a quantifiable HCV RNA will be assessed for treatment based on standard eligibility criteria for government reimbursement of therapy. If eligible, they will be treated as per standard of care with a government approved pan-genotypic HCV DAA treatment. Participants will be encouraged to take the first dose on the day of treatment work-up where possible. On-treatment and post-treatment testing and monitoring will be based on the site investigator as per standard clinical practice.

All HCV RNA positive participants will be followed up at 12 weeks, 24 weeks, and 12 months post HCV RNA test.

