14.0 Statistics

14.1 Hypothesis

Compared to standard of care, an intervention consisting of either dried blood spot testing or point-of-care HCV RNA testing will lead to an increased proportion who initiate HCV treatment at 12 weeks following enrolment among people with HCV who have recently injecting drug use attending NSP services.

Compared to dried blood spot testing, point-of-care HCV RNA testing will lead to an increased proportion who initiate HCV treatment at 12 weeks following enrolment among people with HCV who have recently injecting drug use attending NSP services.

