In the intervention and control arms, the total number tested will be 3,300 [total infected, n=660; total treated, n=165 (n=22 in the control arm, n=44 in the dried blood testing arm, and n=99 point-of-care HCV RNA testing arm)].

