14.5 Statistical analysis

Analysis will follow the CONSORT guidelines for cluster randomised trials²¹. The analysis of the primary outcome will occur when all participants have completed 12 weeks of follow-up or have been permanently lost to follow-up. Participant and cluster flow will be summarised, showing the numbers of clusters and participants randomised and included, and numbers of participants across clusters who complete follow-up with a primary outcome. The primary endpoint will be the proportion of participants who initiate HCV treatment within 12 weeks. Participants who initiate HCV treatment will be traceable, so participants lost to follow-up before initiating HCV treatment will be included in Intention to Treat analyses as having not initiated treatment. Randomised groups will be compared using repeated measures logistic regression methods, clustered on site, fitted using GEE methods with robust standard errors. Secondary analyses will include the proportion linked to care, time to HCV treatment initiation, the proportion initiating HCV treatment by 24 weeks of follow-up, the proportion initiating HCV treatment by the end of follow-up, HCV treatment completion, and response to HCV treatment.

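### Secondary objective 1 compares time to treatment between arms only among those who start it, a selected group that randomisation does not protect

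*Protocol*

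**What the plan says.** The first objective in Protocol section 4.2, repeated in the synopsis, is: "To compare the time to HCV DAA treatment initiation among those who initiate treatment". The comparison is across point-of-care testing, dried blood spot testing and standard of care.

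The other initiation objectives use a wider denominator. The primary objective (section 4.1) is "To compare the proportion of HCV RNA positive participants who initiate HCV treatment at 12 weeks following enrolment", and secondary objectives 2 and 3 use all HCV RNA positive participants at 24 and 52 weeks. In section 14.5, people lost before starting treatment stay in the primary analysis as not having started.

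Section 14.5 also states: "Secondary analyses will include the proportion linked to care, time to HCV treatment initiation". It gives no population or censoring rule for that analysis, so it does not withdraw the restriction in section 4.2.

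The protocol expects the selecting event to differ by arm. Section 14.1 predicts that, relative to dried blood spot testing, "point-of-care HCV RNA testing will lead to an increased proportion who initiate HCV treatment at 12 weeks following enrolment". Section 7.1.4 expects 12-week uptake of 45% (point-of-care), 20% (dried blood spot) and 10% (control). Section 14.3 turns this into expected numbers treated: "n=22 in the control arm, n=44 in the dried blood testing arm, and n=99 point-of-care HCV RNA testing arm".

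**The concern.** Restricting a between-arm comparison to people who start treatment conditions on a post-randomisation event that the intervention is designed to affect. If 10% start in one arm and 45% in another, the two groups of starters need not be alike, even with perfectly balanced clusters. A difference in their starting times then mixes any effect on speed with the difference in who is selected.

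The restricted comparison also ignores the main way a testing strategy can shorten time to treatment, which is by turning people who would not have started into people who do. A strategy that multiplies uptake but leaves the timing among starters unchanged shows no effect on this measure. Objective 1 could therefore report little or no difference in time to treatment for a strategy that greatly accelerates it in the enrolled population.

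**Working it through.** **Inputs from the protocol**
- Expected 12-week uptake: control 10%, dried blood spot 20%, point-of-care 45% (section 7.1.4).
- Enrolment: "Hence a total of 660 HCV RNA positive participants will be enrolled in the study" (section 8.1), which is 220 per condition.
- Expected starters: 22, 44 and 99, total 165 (section 14.3).

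**Step 1: reproduce the protocol's figure.** 220 × 0.10 + 220 × 0.20 + 220 × 0.45 = 22 + 44 + 99 = 165, as stated. At 12 weeks the subset is 165/660 = 25% of those enrolled, and 660 − 165 = 495 (75%) lie outside it. The selection fraction differs 4.5-fold between point-of-care and control (0.45/0.10).

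**Step 2: the effect of a longer window.** Objective 1 has no 12-week limit, and the protocol gives no later uptake rates. As an assumption, take a constant starting rate in each arm, λ = −ln(1 − p)/12 per week: 0.00878 (control), 0.0186 (dried blood spot) and 0.0498 (point-of-care). The proportion starting by 52 weeks, 1 − exp(−52λ), is then 0.367, 0.620 and 0.925. The number excluded falls to about 220 × (0.633 + 0.380 + 0.075) ≈ 240 of 660. The selection still differs by a factor of 0.925/0.367 ≈ 2.5.

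**Step 3: attenuation under the same assumption.** Hazard ratios among all participants are ratios of the λ values: 5.67 (point-of-care vs control), 2.12 (dried blood spot vs control) and 2.68 (point-of-care vs dried blood spot). The median among those starting within a window, with P the proportion starting in it, is −ln(1 − P/2)/λ.

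| Window | Control | Dried blood spot | Point-of-care |
|---|---|---|---|
| 12 weeks | 5.8 weeks | 5.7 weeks | 5.1 weeks |
| 52 weeks | 23.1 weeks | 19.9 weeks | 12.5 weeks |

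The order is right, but at 12 weeks a hazard ratio of 5.67 leaves a difference of only 0.7 weeks.

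**Step 4: an effect missed.** Simulation of 220 control and 220 point-of-care participants, clustering ignored, with uptake of 10% vs 45% and starting times uniform over 0–12 weeks in both arms. A rank-sum test among starters rejects in 5% of 2,000 runs, which is its nominal error rate. A log-rank test among all participants, censored at 12 weeks, rejects in all of 200 runs.

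**Step 5: can it reverse?** Assume control starts 10% uniformly over weeks 0–6, and point-of-care starts the same 10% plus a further 35% uniformly over weeks 4–12. Cumulative initiation under point-of-care is never below control. The control median among starters solves 0.10x/6 = 0.05, so x = 3.0 weeks. The point-of-care median solves 0.10 + 0.35(x − 4)/8 = 0.225, so x = 6.9 weeks. In simulation the starters-only test is significant in the wrong direction in all 2,000 runs. This pattern was chosen to show that reversal is possible. It is not a protocol figure.

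**The case against.** The case on the other side has real substance.

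- **Window.** A reader might infer that objective 1 conditions on the primary outcome itself. It does not: the primary outcome is initiation by 12 weeks and objective 1 sets no limit. It is the same kind of event over a longer window. For the same reason, 75% excluded is a 12-week planning figure and an upper bound under the planning rates. This narrows the size but leaves the selection in place.
- **Reversal.** A reader might infer that point-of-care testing is likely to look slower. The documents do not support that. They plan same-day results where possible (section 10.2), work-up on the screening day (section 7.1.4) and encouragement to take the first dose on the day of work-up (section 8.1). Under constant rates the starters-only medians keep the right order. Nor does the protocol say that starters in the control arm are the most motivated.
- **Information already planned.** Comparisons at 12, 24 and 52 weeks on the full denominator give three points on the cumulative initiation curve. That limits the harm, because a misleading starters-only result would sit beside them. It does not make the stated comparison valid.
- **Deferral to the SAP.** Methods for secondary endpoints are often left to the SAP, which is not at hand. Here, though, the protocol's objective itself fixes the population, and it uses the verb for a between-arm comparison rather than a description.
- **The remedy has its own difficulties.** Same-day starts produce ties at day 0. Proportional hazards is doubtful between a same-day and a referral pathway. Untreated controls may be re-screened into the intervention phase from 3 months (section 10.6), so censoring them then may be informative. These points stand and shape the fix.

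**Conclusion.** The concern holds for secondary objective 1. As written, it is a between-arm comparison in subsets defined by a post-randomisation event expected to occur in 10%, 20% and 45% of participants by 12 weeks. Randomisation does not protect that contrast.

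The better-supported consequence is attenuation or a missed effect. The sizes shown rest on assumed timing distributions (constant rates or uniform starting times) and ignore clustering and the stepped design. That the subsets are differently selected rests only on the protocol's own uptake figures.

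A reader might also infer that the trial's main result is compromised. It is not: the primary analysis keeps non-starters in the denominator. This is a point about one secondary objective that should be corrected.

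**What to change.** Reword objective 1, in section 4.2 and the synopsis, as time from enrolment to DAA initiation among all HCV RNA positive participants, with non-starters kept at risk and censored at the end of follow-up. This fits the unrestricted listing in section 14.5 and the denominator of objectives 2 and 3.

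- Report cumulative initiation curves by arm, with a site-clustered comparison that does not rest on proportional hazards alone and allows for ties at day 0.
- For controls, either limit the main comparison to the first 12 weeks, before re-screening opens at 3 months, or follow longer and treat censoring at re-screening as potentially informative in a sensitivity analysis.
- Keep the median time among starters, labelled as descriptive.

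The cost is a wording change and a little more analysis work. No new data are needed: section 9.1 already has the first-dose date recorded for all HCV RNA positive participants, and section 14.5 states that those who start treatment can be traced.

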5.0 Study setting

This study will be conducted at 22 primary NSP in Australia. It is estimated that each site will consent and screen 100-120 participants for HCV infection, of which an estimated 20-30 HCV RNA positive participants per site will enrol (based on an HCV RNA prevalence of 20%). Depending on recruitment rate, some sites may enrol more than 20 HCV RNA positive participants.

6.0 Participant population

It is anticipated that approximately 3,300 participants (assuming an HCV RNA prevalence of 20%) will be screened for HCV infection using either dried blood spot testing, point-of-care testing or standard of care testing.

Screening in the intervention arm will continue until a total of 220 HCV RNA positive participants (~20 participants per site) are enrolled in the intervention arm (either dried blood spot and point-of-care). In the delayed intervention arm, 220 HCV RNA positive participants (~20 participants per site) will be enrolled in the control (standard of care) phase and then clusters/sites will be switched to intervention (either dried blood spot and point-of-care) – at which screening will continue until a total of 220 HCV RNA positive participants (~20 participants per site) are enrolled. Hence a total of 660 HCV RNA positive participants.

7.0 Eligibility criteria

7.1.1 Identification and inclusion criteria for clusters

NSPs must meet the following criteria to participate in the study:

- a. Be a primary NSP site, defined as, providing services to PWID staffed by specialist workers
- b. Have the capacity for on-site nursing support or externally, and HCV treatment provision
- c. Provide services to > 60 people per week.

Potential eligible NSP sites will be identified from existing service centres in Australia and will complete site feasibility assessment to ensure the inclusion criteria are met. NSP sites may have prior experience or are active in surveillance and clinical studies, but it is not mandatory to have clinical research experience.

7.1.2 Inclusion criteria for participants

Attendees of the NSP service are eligible for inclusion if the following criteria are met:

- a. Provided written informed consent
- b. ≥ 18 years of age
- c. Recent injecting drug use defined as self-reported use within the previous six months.

7.1.3 Exclusion criteria for participants

Attendees of the NSP service are not eligible for inclusion if any of the following exclusion criteria are met:

 a. Is unable or unwilling to provide informed consent or abide by the requirements of the study.

